8. GENERAL ISSUES FOR STATISTICAL ANALYSES

8.1 Adjustment for Covariates

The log-transformed antibody titers at Day 29 and Day 181 will be analyzed using an Analysis of Covariance (ANCOVA) model which includes the log-transformed pre-vaccination antibody titer, age subgroup stratification (50 - 64, ≥ 65 years) and previous vaccination history stratification (no in previous 3 years, yes). Summary tables will show both adjusted and unadjusted GMTs for each vaccine group and adjusted and unadjusted GMT ratio for aQIVc versus each of the other three vaccine groups.

The main analysis of binary immunogenicity endpoints ((i.e., percentages of subjects with seroconversion and with titer \geq 1:40) will not be adjusted for any of the covariates. Binary data will be summarized for each group using unadjusted estimates and will be reported together with two-sided exact 95% CIs. Sensitivity analysis may be done to include the stratification factors age and previous vaccination history as covariates in a generalized linear model.

8.2 Handling of Dropouts, Missing Data

The distribution of subjects with reasons for missing immunogenicity values will be described by vaccine group. Key baseline characteristics, such as age and previous vaccination history, will be compared between the subjects with immunogenicity values and those who have missing data. For immunogenicity data, it may be reasonable to consider missing immunogenicity values as missing completely at random (MCAR), i.e., not informative.

Therefore, the immunogenicity analysis will comprise a complete case analysis only, without introducing any bias. Additional sensitivity analysis will be considered if the percentage of subjects with missing data is more than 10%.

Solicited adverse events are collected using electronic diaries from Day 1 to Day 7 postvaccination. If data have not been recorded for all 7 days, the assessment is considered missing and excluded from the safety analysis. In case, at least one day is filled in but other days are missing the presence or absence of the event will be based on the available data. If more than 5% of the subjects have incomplete diary data, additional tables for solicited adverse events will be created based on complete diary card data. The number of days and number of subjects with missing data will be tabulated by treatment group.

8.3 Multicenter Studies

Stratification is used on two important factors related to the immunogenicity endpoints: age and previous vaccination history. These factors will be included in the statistical model.

Centers will not be used as stratification factor and will not be included in the statistical analysis.

8.4 Multiple Comparisons and Multiplicity

This a phase 2, exploratory study and no adjustment will be applied for multiple endpoints and multiple comparisons.

8.5 Subgroups

All analyses (safety and immunogenicity) will be done by the age subgroups 50-64 years or ≥ 65 years.

Unadjusted immunogenicity analysis of the GMTs will be performed by stratifying for the following subgroups:

- Influenza vaccination history previous 3 years as yes and no;
- Comorbidity risk (yes/no) defined as Hak score < 50 or ≥ 50 ;
- Sex;

Exploratory interaction analyses may be conducted to support consistency or lack of consistency of the results among the subgroups.

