#### **Statistical Analyses:**

The primary analysis will be conducted on the immunogenicity and safety data collected up to Day 29. Exploratory comparisons of HI Geometric Mean Titer (GMTs) and MN

Print Date (Local): 30-mrt-2020 10:41:00

GMTs between treatment groups will be performed through the computation of the two-sided 95% confidence interval (CI) of the vaccine group ratio of GMTs:

*GMTs aQIVc / GMTs comparator groups*

To estimate the GMT ratio (adjusted analysis), a general linear model (GLM) will be fitted on log-transformed (base ten) post-vaccination HI titer as the outcome variable and terms for covariates: vaccine treatment, log 10 transformed pre-vaccination HI titer, age stratum, and vaccination history. Potential covariate interaction effects will also be examined in the fit of the GLM. From the model, an adjusted difference in the least square means (on the log scale) will be produced with 95% confidence limits. The estimated difference and the confidence limits will be back-transformed to obtain an *adjusted GMT ratio* with 95% confidence limits. Each of the four strains will be analyzed separately.

The difference in seroconversion rates (SCRs) or percentage of subjects with HI titer  $\geq 1:40$  will be presented with 95% CIs using the Miettinen and Nurminen method without and with adjustment for the age stratum. Each of the four strains will be analyzed separately.

Additionally, exploratory comparisons between groups will be performed through the computation of the two-sided 95% CI for the difference in the percentages between aQIVc vaccine and comparator groups.

Statistical Considerations for Sample Size Calculations:

A total of 480 subjects (including a 10% drop-out rate) will be enrolled in this study and are to be randomized in a 1:1:1:1 ratio to one of the four vaccine groups. Approximately one hundred twenty subjects will be enrolled in each vaccine group. More details on the sample size calculation are provided in [Section 8.5](#).

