##### 8.4.2.2.3 Statistical Methods

All statistical analyses for HI (and MN) titers will be performed on the logarithmically (base 10) transformed values. Individual HI titers below the detection limit (<10) will be set to half of that limit (5); values above the upper limit of quantification will be set to the upper limit.

Print Date (Local): 30-mrt-2020 10:41:00

Reverse cumulative distribution curves will be derived by time-point and strain.

Crude estimates for GMTs, GMFIs and pertaining 2-sided 95% CIs will be calculated assuming a log-normal distribution of the titers and will be completed by providing minimum, maximum and median titers for each vaccine group. Binary data (i.e., percentages of subjects with seroconversion and with titer  $\geq 1:40$ ) will be summarized for each group using crude estimates and will be reported together with 2-sided 95% CIs calculated according to Clopper Pearson's method. No multiplicity adjustment to the CI levels will be implemented.

For immunogenicity data, it may be reasonable to consider missing immunogenicity values as missing completely at random (MCAR), i.e., not informative. Therefore, the immunogenicity analysis will comprise a complete case analysis only, without introducing any bias.

The analysis model for the HI GMT will be done using a general linear model on log-transformed (base 10) Day 29 titers as the outcome variable and as covariates: treatment groups (aQIVc, QIVc, aQIV, and QIVr), pre-vaccination titer, age stratum. From this model, adjusted differences in the least square means (on the log scale) will be produced with 95% confidence limits for aQIVc versus QIVc, for aQIVc versus aQIV and for aQIVc versus QIVr. The estimated difference and the confidence limits will be back-transformed to obtain an *adjusted GMT ratio* with 95% confidence limits. Each of the four strains will be analyzed separately.

Potential interaction between age stratum and treatment effect will be examined, as well as the other co-variates such as previous vaccination history and age were taken as a continuous factor.

A similar model will be used for the GMFI on Day 29.

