The analysis model used for the comparison of the HI (or MN) GMT between aQIVc and the other three vaccine groups will be done using a general linear model on log-transformed (base 10) Day 29 titers as the outcome variable and as covariates: treatment groups (aQIVc, QIVc, aQIV, and QIVr), log-transformed pre-vaccination titer, age subgroup and previous vaccination history. From this model, adjusted differences in the least square means (on the log scale) will be produced with 95% confidence limits for aQIVc versus QIVc, for aQIVc versus aQIV and for aQIVc versus QIVr. The estimated difference and the confidence limits will be back-transformed to obtain an *adjusted GMT ratio* with 95% confidence limits. Each of the four strains will be analyzed separately.

The same analysis model, except excluding the factor age subgroup, will be run for each age subgroup separately and and present all adjusted GMT ratios with 95% confidence intervals for each age subgroup.

Additional exploratory analysis will be considered using age as continuous covariable including the assessment of interaction between age and treatment group.

Unadjusted GMT ratio will be based on a simple ANOVA model on the log-transformed titers and the treatment group.

Geometric Mean Fold Increase

Summary statistics (geometric mean, 95% confidence interval of GMT, minimum, median, maximum) of the relative increase in titers will be presented by assessment (Day 29), strain and vaccine group.

The analysis model for the fold increase in titers will be done using the same models as mentioned above on log-transformed (base 10) (Day 29 titers/Day 1 titers) as the outcome variable but excluding the log-transformed pre-vaccination titer.

16 MAR 2021 Final Version 2.0

Analysis of binary endpoints

The number and proportion of subjects achieving the binary endpoints (seroconversion or HI titer >=1:40) will be summarized by assessment (Day 29), strain and vaccine group.

For each of the influenza vaccine strains and for each of the vaccine groups, summaries will include the associated two-sided 95% confidence intervals according to Clopper-Pearson.

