16. CHANGES TO PLANNED ANALYSIS

Compared to the final protocol, one optional exploratory analysis has been added on the comparability of the cell-based and egg-based titers. Details will be described in a separate analysis plan. For the primary endpoints, the GMT and the % of subjects with HI >=1:40, Day 1 was added to assure that we include the pre-vaccination results.

The statistical analysis plan was amended before unblinding. The following changes since version 1.0 16 Jun 2020 were made:

Section	Change	Rationale
8.7	Unsolicited adverse events before	This was requested by the US
	vaccination will be mapped to medical	regulatory agency (FDA CBER).
	history	
11.2	Analysis of GMT ratio: Adjusted estimates	All subgroup analyses, including the
	of GMT ratio by age subgroup will be	age subgroup, will be conducted in a
	calculated using the same model excluding	similar way by subgroup.
	the factor age subgroup.	
11.2	Analysis of binary endpoints: Additional	Factor pre-vaccination titer was
	supportive analyses will be done using	removed from the model due
	generalized linear models without the factor	expected convergence issue leading
	for pre-vaccination titer.	to non-estimable treatment effects.
13.2	Clarification added that the temperature will	Needed for programming to apply
	be converted to °C in one decimal.	the grading for the temperature

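### SAP 8.5 plans only unadjusted GMT analyses for the vaccination-history, Hak-risk and sex subgroups, although the Day 1 titre is in the GMT model overall and within each age subgroup

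*SAP*

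**What the plan says.** SAP 8.5 requires all analyses by age subgroup. It then treats three other factors (vaccination history in the previous 3 years, Hak score below 50 or at least 50, and sex) differently: "Unadjusted immunogenicity analysis of the GMTs will be performed by stratifying for the following subgroups". The only other analysis it offers for them is optional: "Exploratory interaction analyses may be conducted to support consistency or lack of consistency of the results among the subgroups".

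Elsewhere the Day 1 titre is used. SAP 8.1 describes an ANCOVA with log pre-vaccination titre, age subgroup and vaccination history, and adds: "Summary tables will show both adjusted and unadjusted GMTs for each vaccine group". It plans adjusted and unadjusted GMT ratios of aQIVc against each comparator in the same tables. SAP 11.2 repeats that model for Day 29 and carries it into the age subgroups: "The same analysis model, except excluding the factor age subgroup, will be run for each age subgroup separately". The Day 1 titre therefore stays in. SAP 11.2 bases the unadjusted ratio on an ANOVA with treatment group alone.

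**The concern.** The Day 1 sample is drawn from every subject, and the adjusted model is already specified and will be programmed. Leaving the Day 1 titre out in three subgroup families discards information the trial has paid for, in the parts of the data that are thinnest.

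Three things are at stake:

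- **Precision.** Intervals for aQIVc against a comparator are wider than they need be.
- **Chance imbalance.** A Day 1 difference between arms is more likely to be sizeable in a small subgroup. SAP 11.2 tabulates Day 1 GMTs by vaccine group, so an imbalance may be visible, but no subgroup result corrects for it.
- **Comparability.** A reader would set unadjusted subgroup results beside adjusted overall and age-subgroup ratios, and could not tell a subgroup difference from a change of method.

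Vaccination history matters most. It is a stratification factor, SAP 8.3 treats it as important for immunogenicity, and Protocol 8.3.7 names it as the one additional subgroup.

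**Working it through.** **Inputs**

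- n = 108 per arm after 10% drop-out, and SD of log10 titre from 0.45 to 0.80 (SAP 5, Table 2).
- About 40% per arm not previously vaccinated (SAP 4.1): 0.40 × 108 ≈ 43 per arm, leaving 0.60 × 108 ≈ 65 previously vaccinated.
- r, the within-arm correlation of Day 1 and Day 29 log titres: not in the documents, so a range is assumed.
- Subgroup SD taken equal to the overall SD (assumed). Sex and Hak subgroup sizes are not in the documents.

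**The plan's own figure**

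CI half-width on the log10 scale = t × SD × √(2/n). For n = 108, SD 0.45 and 214 degrees of freedom this is 0.1207, so the multiplier is 10^(±0.1207) = 0.76 to 1.32. SD 0.80 gives 0.61 to 1.64. Both match SAP Table 2, which includes no baseline adjustment and no subgroup sizes.

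**Effect of omitting the Day 1 titre**

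Adjustment reduces the residual SD to SD × √(1 − r²), so unadjusted SE / adjusted SE = 1/√(1 − r²):

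| r | SE ratio | Excess |
|---|---|---|
| 0.2 | 1.021 | 2% |
| 0.3 | 1.048 | 5% |
| 0.5 | 1.155 | 15% |
| 0.7 | 1.400 | 40% |

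**Intervals by vaccination history**

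The multiplier is 10^(± t × SD × √(1 − r²) × √(2/n)). Error degrees of freedom are 4n − 4 unadjusted and 4n − 6 with Day 1 titre and age in the model. For example, with n = 43, SD 0.45 and r = 0.5: 1.974 × 0.45 × 0.866 × 0.2157 = 0.166, and 10^(±0.166) = 0.68 to 1.47.

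| Subgroup, SD | Unadjusted | r = 0.3 | r = 0.5 | r = 0.7 |
|---|---|---|---|---|
| Not vaccinated (43/arm), 0.45 | 0.64–1.55 | 0.66–1.52 | 0.68–1.47 | 0.73–1.37 |
| Not vaccinated (43/arm), 0.80 | 0.46–2.19 | 0.47–2.11 | 0.51–1.97 | 0.57–1.75 |
| Vaccinated (65/arm), 0.45 | 0.70–1.43 | 0.71–1.41 | 0.73–1.36 | 0.77–1.29 |

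**r within a history stratum may be lower**

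If history explains 20% of both Day 1 and Day 29 variance in the same direction (assumed), within-stratum r = (r − 0.2)/0.8. Overall r of 0.3, 0.5 and 0.7 become 0.125, 0.375 and 0.625, and the SE excess falls to about 1%, 8% and 28%.

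**Chance Day 1 imbalance**

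With 43 per arm and SD 0.60, one standard error of the Day 1 difference is 0.60 × √(2/43) = 0.129 log10. With equal SDs on both days and r = 0.5 (assumed), it shifts an unadjusted ratio by 0.5 × 0.129 = 0.065 log10, a factor of 1.16.

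**If r is zero**

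In simulated four-arm trials (3,000 per setting), adjusting for Day 1 titre and age at r = 0 widened the interval by about 0.3% at 43 per arm and 1.4% at an assumed 10 per arm. Neither estimator showed bias: the mean error was at most 0.005 log10.

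**The case against.** The strongest reply is that SAP 8.5 speaks of GMTs, and SAP 8.1 uses GMTs and GMT ratios as separate terms. Read literally, SAP 8.5 promises only per-arm summaries, and every interval above concerns a ratio it may not print. This narrows the point without removing it: SAP 8.1 plans adjusted per-arm GMTs as well, and SAP 11 makes aQIVc against each comparator the focus of the immunogenicity analysis.

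Second, age has a special claim, because the objectives name the two age groups. Hak risk and sex are not protocol subgroups, and Protocol 8.3.7 leaves the details for vaccination history to the SAP. Simple summaries are defensible in a descriptive study with no hypothesis test or success criterion. That stands, and it keeps the point minor.

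Third, r is unknown, and at 0.3 or below the interval barely moves. That also stands.

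Two stronger readings are tempting, but the documents do not support them:

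- **That SAP 16 contradicts SAP 8.5.** The rationale for the age-subgroup change begins "All subgroup analyses, including the" and ends "similar way by subgroup". A reader might infer a promise of the same covariates everywhere. It is a rationale cell in a table of changes, and it can mean only that analyses are run separately within each subgroup, which SAP 8.5 also does.
- **That the protocol commits to an adjusted vaccination-history analysis which the SAP withdrew.** Protocol 8.4.2.2.3 says "Potential interaction between age stratum and treatment effect will be examined, as well as the other co-variates such as previous vaccination history", but the sentence goes on ungrammatically to age as a continuous factor. It may mean only that history is tried as a covariate, which SAP 11.2 does. The synopsis is clearer: "Potential covariate interaction effects will also be examined in the fit of the GLM". Its firm wording against the optional wording in SAP 8.5 is a side query about text. It does not show that unadjusted subgroup GMTs are wrong.

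**Conclusion.** The point holds as a minor one. SAP 8.5 commits three subgroup families to unadjusted GMT analyses while the same plan adjusts for the Day 1 titre overall and by age subgroup, and it gives no reason for the difference. A reader might infer bias, but randomisation rules that out, and the main adjusted ratio does not change.

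The cost in precision is negligible at r of 0.2 or below, modest at 0.5 (SE about 15% larger, or about 8% within a history stratum under the 20% assumption) and material at 0.7 (40%, or 28%). These figures rest on an assumed r, on equal SDs across subgroups, and on between-arm ratios being shown or read off. Effects in the Hak and sex subgroups cannot be sized from the documents.

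**What to change.** Add to SAP 8.5, in substance: for Day 29 HI, adjusted GMTs and adjusted GMT ratios of aQIVc to each comparator, with 95% CIs from the Section 11.2 model, will be shown beside the unadjusted results in the vaccination-history, Hak-risk and sex subgroups. Vaccination history is left out of the model where it defines the subgroup.

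The text should also fix before unblinding the rule for dropping the age factor in sparse cells, for instance a minimum count pooled over arms, so that the model is not chosen from the data by arm. Hak score of at least 50 is the likely case: that score gives points for age only from 70, so few subjects aged 50–64 may reach it. In the same edit, say whether the vaccination-history interaction will be examined or only may be.

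The cost is two or three sentences, with the same data and model code and no extra visits or subjects. The downside is 6 subgroup levels × 4 strains × 3 comparators = 72 added exploratory ratios without multiplicity adjustment. Extending this to HI and MN at Days 29 and 181 would make it 72 × 2 × 2 = 288, which is why the addition is limited to Day 29 HI.

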8.6 Data Transformation

Distributions of antibodies are generally skewed to the right and approximately log-normally distributed. Therefore, prior to any statistical analysis that assumes normally distributed observations, antibody titers will be log₁₀-transformed. GMTs and their 95% CIs will be then computed by exponentiating (base 10) the means and 95% CIs of the log₁₀ transformed titers.

8.7 Derived and Computed Variables

Demographics

In the case that Age and/or Body Mass Index must be recomputed by standard software

Age will be calculated in years using the following formula:

Integer [(Date of Visit 1 - Date of Birth + 1) / 365.25]

Body Mass Index (kg/m²) will be calculated using the following formula:

Mass (kg) / Height² (m²)

The total HAK score will be derived by the sum of all scores (see protocol appendix 1). The total HAK score will be categorized as a score < 50 or ≥ 50 .

Immunogenicity

Values below the lower limit of quantification will be set to half that limit. Values above the upper limit of quantification will be set to the value of this upper limit.

Seroconversion based on **HI** antibodies is defined as binary variable for subjects with non-missing values pre-vaccination- and post-vaccination as:

= 1, if seroconverted (defined as $a \ge 4$ -fold increase in titer post-vaccination in those with prevaccination titer above the LLOQ (1:10), or a post-vaccination titer $\ge 1:40$ for subjects with prevaccination titer below the LLOQ (1:10))

= 0, otherwise

Seroconversion based on **MN** antibodies is defined as binary variable for subjects with nonmissing values pre-vaccination- and post-vaccination as:

= 1, if seroconverted (defined as a \geq 4-fold increase in titer post-vaccination in those with prevaccination titer above the LLOQ, or a post-vaccination titer \geq 4 times the LLOQ for subjects with pre-vaccination titer below the LLOQ

= 0, otherwise

Statistical Analysis Plan, Protocol Number V200_10 16 MAR 2021 Final Version 2.0

Fold increase is defined as the post-vaccination titer divided by the pre-vaccination titer.

Geometric Mean Titer

The GMT will be calculated using the following formula:

$$\mathbf{0}^{\left\{\frac{\sum_{i=1}^{n}\log_{10}\left(t_{i}\right)}{n}\right\}}$$

1

where $t_1, t_2, ..., t_n$ are *n* observed immunogenicity titers. The 95% confidence intervals for GMT will be calculated as $10^{\{M-t_{0.975,n-1}SE\}}$, $10^{\{M+t_{0.975,n-1}SE\}}$; where M and SE are the means and standard error of logarithm base 10 -transformed titers, respectively.

Solicited Adverse Events

For details see section 13.2.

Unsolicited Adverse Events

All adverse events will be characterized according to the date of occurrence related to the vaccination. If the start date is before the date of injection of study vaccine or indicated as on injection day but before injection, these events will not be considered as unsolicited adverse events and mapped to the medical history.

Note: If an adverse event start date is missing or unknown and no indication is provided on the timing, the adverse event will be considered as emergent.

When start and/or end dates of an adverse event are only partially known, adverse events will be categorized as emergent before, during, or after vaccination phase using the following rules:

• If the partial end date is before (<) the vaccination (i.e., year or year & month is/are before the study vaccination year or year & month) then the adverse event is pre-vaccination and the event will be mapped to the medical history.

16 MAR 2021 Final Version 2.0

• If the partial start date is equal or after (≥) the first study vaccination (i.e., year or year and month is/are after or the same as the first study injection year or year and month) then the adverse event is emergent during vaccination phase.

All adverse events emergent during vaccination phase will categorized as occurring during the period of 28 days following vaccination based on the start date. If start date is missing or incomplete, events will be counted as yes during the period of 28 days following vaccination.

The **maximum event severity** is the greatest severity associated with a preferred term (PT) for a reported adverse event according to the following order: Mild < Moderate < Severe.

Vaccination-related Adverse Events are those for which the cause has been evaluated by the investigator, and recorded as possibly related, probably related or unknown/ missing.

Prior and Concomitant Medications

All medications will be characterized according to the start and end date of occurrence related to the vaccination as follows:

- **Pre-vaccination**: start date before the date of injection of study vaccine.
- **Concomitant:** start date before vaccination but continued after vaccination or start date after vaccination. The period Day 1- 29 will be labeled if in addition, the start date is on or before Day 29.

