### 8.1.1.1 Primary Immunogenicity Endpoints

Humoral immune response in terms of HI antibody response against homologous *cell-derived* vaccine strains (A/H1N1, A/H3N2, B/Yamagata and B/Victoria):

- Geometric Mean Titer (GMT): Geometric mean of HI antibodies at Day 29;
- Geometric Mean Fold Increase (GMFI): The Geometric mean of the fold increase in serum HI GMTs post-vaccination (Day 29) compared to pre-vaccination (Day 1);
- Percentages of subjects with HI titers  $\geq 1:40$  at Day 29;
- Percentage of subjects with seroconversion (defined as a  $\geq 4$ -fold increase in titer post-vaccination in those with pre-vaccination titer above the LLOQ (1:10), or a post-vaccination titer  $\geq 1:40$  for subjects with baseline titer below the LLOQ (1:10) for HI antibodies at Day 29).

Note that the HI assay could be replaced by the MN assay due to a lack of agglutination.

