### 8.1.2.2 Secondary Immunogenicity Endpoints

Humoral immune response in terms of HI antibody response against homologous *cell-derived* vaccine strains (A/H1N1, A/H3N2, B/Yamagata and B/Victoria) at Day 181:

- GMT: Geometric mean of HI antibodies at Day 181;
- GMFI: The Geometric mean of the fold increase in serum HI GMTs post-vaccination (Day 181) compared to pre-vaccination (Day 1);
- Percentages of subjects with HI titers  $\geq 1:40$  on Day 181.

In addition, the humoral immune response in terms of MN antibody response against homologous *cell-derived* vaccine strains (A/H1N1, A/H3N2, B/Yamagata and B/Victoria) at Days 29 and 181:

- GMT: Geometric mean of MN antibodies at Days 29 and 181;
- GMFI: The Geometric mean of the fold increase in serum MN GMTs post-vaccination (Day 29 and Day 181) compared to pre-vaccination (Day 1);
- Percentages of subjects with seroconversion (defined as  $\geq 4$ -fold increase for subjects with pre-vaccination MN titers  $\geq$  Lower Limit of Quantitation (LLOQ) or as  $\geq 4$ LLOQ for subjects with pre-vaccination MN titer <LLOQ) at Day 29.

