11.2 Primary Objectives Analysis

The primary endpoints in terms of HI antibody response against homologous cell-derived vaccine strains (A/H1N1, A/H3N2, B/Yamagata and B/Victoria) are defined as:

- Geometric Mean Titer (GMT): Geometric mean of HI antibodies at Day 29 and Day 1;
- Geometric Mean Fold Increase (GMFI): The Geometric mean of the fold increase in serum HI GMTs post-vaccination (Day 29) compared to pre-vaccination (Day 1);
- Percentages of subjects with HI titers \geq 1:40 at Day 29 and Day 1;
- Percentage of subjects with seroconversion (defined as $a \ge 4$ -fold increase in titer post-vaccination in those with pre-vaccination titer above the LLOQ (1:10), or a post-vaccination titer $\ge 1:40$ for subjects with baseline titer below the LLOQ (1:10) for HI antibodies at Day 29).

Note that the HI assay could be replaced by the MN assay due to a lack of agglutination.

In addition, reverse cumulative distribution plots will be generated to display the distribution of the antibody responses at Day1 and Day 29 for each of the vaccine groups. The x-axis represents the immunogenicity values, and the scale of the axis is logarithmic. The y-axis represents the percentage of subjects having at least that immunogenicity value. Due to the discrete values of antibody response, the plot will show a step-wise function. The figures begin at 100%, and then descends to the lowest point on the curve, which is the percentage of subjects having an immunogenicity value equal to the highest observed value.

No hypothesis testing will be applied.

Effective Date: See System Metadata

16 MAR 2021 Final Version 2.0

Geometric Mean Titer

Summary statistics (geometric mean, 95% confidence interval of GMT, minimum, median, maximum) of the titers will be presented by strain, assessment (Day 1 or Day 29) and vaccine group.

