11.3 Secondary Objectives Analysis

The secondary endpoints in terms of HI antibody response against homologous cell-derived vaccine strains (A/H1N1, A/H3N2, B/Yamagata and B/Victoria) at Day 181, are:

- GMT: Geometric mean of HI antibodies at Day 181;
- GMFI: The Geometric mean of the fold increase in serum HI GMTs post-vaccination (Day 181) compared to pre-vaccination (Day 1);
- Percentages of subjects with HI titers \geq 1:40 on Day 181.

In addition, the humoral immune response in terms of MN antibody response against homologous cell-derived vaccine strains (A/H1N1, A/H3N2, B/Yamagata and B/Victoria) at Days 29 and 181:

- GMT: Geometric mean of MN antibodies at Days 29 and 181;
- GMFI: The Geometric mean of the fold increase in serum MN GMTs post-vaccination (Day 29 and Day 181) compared to pre-vaccination (Day 1);
- Percentages of subjects with seroconversion (defined as ≥ 4-fold increase for subjects with prevaccination MN titers ≥ Lower Limit of Quantitation (LLOQ) or as ≥ 4*LLOQ for subjects with pre-vaccination MN titer <LLOQ) at Day 29.

16 MAR 2021 Final Version 2.0

The analysis of the secondary immunogenicity endpoints will be conducted in the same way as described for the primary immunogenicity endpoints.

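### As written, the seroconversion rule in SAP 8.7 counts a subject with a baseline titre exactly at the LLOQ (HI 1:10) as a non-responder whatever the rise, and its MN version conflicts with SAP 11.3

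*SAP*

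**What the plan says.** **HI.** SAP 8.7 defines seroconversion as a binary variable with two routes to a value of 1: a fourfold or greater "increase in titer post-vaccination in those with prevaccination titer above the LLOQ (1:10), or a post-vaccination titer" of at least 1:40 when the baseline is below 1:10. All other subjects with both titres available get 0. The endpoint definition in SAP 11.2 uses the same split, "in those with pre-vaccination titer above the LLOQ (1:10), or a post-vaccination titer", and so does Protocol 8.1.1.1.

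**Values at the limit.** SAP 8.7 states: "Values below the lower limit of quantification will be set to half that limit". Protocol 8.4.2.2.3 gives the HI figures: "Individual HI titers below the detection limit (<10) will be set to half of that limit (5"). Neither rule touches a titre equal to the limit.

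**MN.** SAP 8.7 credits a fourfold rise "in those with prevaccination titer above the LLOQ, or a post-vaccination titer" of at least four times the LLOQ when the baseline is below it, again with 0 for the rest. SAP 11.3 words the upper branch differently: a fourfold "increase for subjects with prevaccination MN titers ≥ Lower Limit of Quantitation (LLOQ"). Protocol 8.1.2.2 also includes the LLOQ in its upper branch, and reserves the criterion of four times the LLOQ "for subjects with pre-vaccination MN titer <LLOQ) at Day 29".

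**Link to the primary endpoints.** Protocol 8.1.1.1 says: "Note that the HI assay could be replaced by the MN assay due to a lack of agglutination". SAP 11.2 carries the same note.

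**The concern.** The two HI branches do not cover every baseline value. A subject measured at exactly 1:10 falls between them and takes the default of 0, so a rise from 1:10 to 1:2560 would be recorded as no seroconversion. This is the lowest quantifiable HI titre and not an exotic value.

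Day 29 HI seroconversion is one of the four primary endpoint types. The derived variable feeds the Clopper-Pearson rates, the Miettinen-Nurminen differences, the supportive generalized linear models and the separate age-group analyses in SAP 11.2. The error runs one way only: true responders are counted as non-responders.

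For MN, the SAP also contradicts itself. A programmer working from 8.7 and another working from 11.3 would produce different variables. If MN replaces HI for a strain that does not agglutinate, the conflict could reach a primary endpoint.

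**Working it through.** The plan states no figure on this point, so there is none to reproduce. The check codes the rules literally and compares them, with *b* the baseline titre and *p* the post-vaccination titre.

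**1. The rules**

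- HI as written (SAP 8.7, SAP 11.2, Protocol 8.1.1.1): 1 if (*b* > 10 and *p*/*b* ≥ 4) or (*b* < 10 and *p* ≥ 40); otherwise 0.
- HI corrected: the same, with *b* ≥ 10 in the first branch.
- MN in SAP 8.7: 1 if (*b* > LLOQ and *p*/*b* ≥ 4) or (*b* < LLOQ and *p* ≥ 4 × LLOQ); otherwise 0.
- MN in SAP 11.3 and Protocol 8.1.2.2: the same, with *b* ≥ LLOQ in the first branch.

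**2. HI comparison.** The documents do not give the dilution series, so a two-fold scale is assumed: 5, 10, 20, … 2560. That is 10 values and 100 baseline/post pairs. The two HI rules differ in exactly 7 pairs, all with a baseline of 10:

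| Baseline | Post-vaccination titre | As written | Corrected |
|---|---|---|---|
| 10 | 5, 10, 20 | 0 | 0 |
| 10 | 40, 80, 160, 320, 640, 1280, 2560 | 0 | 1 |

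**3. Which branch should take 1:10?** At *b* = 10, a fourfold rise is 4 × 10 = 40, which is the lower branch's threshold. Placing 10 in either branch gives identical coding in all 100 pairs.

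**4. MN comparison.** The documents give no MN LLOQ. With assumed values of 10, 20 and 40, the SAP 8.7 and SAP 11.3 rules differ in 7 pairs each time. All have baseline equal to the LLOQ and post titre at least four times the LLOQ; 8.7 gives 0 and 11.3 gives 1.

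**5. Effect on one arm's rate.** Understatement = *s* × *r*, where *s* is the share of the arm at exactly 1:10 and *r* is the proportion of those who reach 1:40 or more. Both are assumptions, because no baseline distribution is given.

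| *s* | *r* = 30% | *r* = 50% | *r* = 70% |
|---|---|---|---|
| 0% | 0 | 0 | 0 |
| 2% | 0.6 points | 1.0 | 1.4 |
| 5% | 1.5 | 2.5 | 3.5 |
| 10% | 3.0 | 5.0 | 7.0 |
| 20% | 6.0 | 10.0 | 14.0 |

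If *r* were as high as 90%, the 20% row would reach 18 points.

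In subjects, using n = 108 per group (SAP section 5): 10% × 108 = 10.8 at 1:10, of whom 10.8 × 0.3 = 3.2 to 10.8 × 0.7 = 7.6 would be miscoded. For an age group of about 108/2 = 54 per arm: 5.4 at 1:10, of whom 1.6 to 3.8 would be miscoded.

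**6. Effect on a between-arm difference.** With equal shares in both arms, the change is *s* × (*r*₁ − *r*₂).

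- *s* of 2% to 20% and response rates 5 to 15 points apart: 0.02 × 5 = 0.1 to 0.20 × 15 = 3.0 points.
- *s* of 5% to 20% and response rates 20 to 30 points apart: 0.05 × 20 = 1.0 to 0.20 × 30 = 6.0 points.
- Equal response rates: no change.

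**7. Comparison with sampling error.** The approximate 95% half-width is 1.96 × √[*p*₁(1 − *p*₁)/108 + *p*₂(1 − *p*₂)/108].

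- Rates 0.5 and 0.4: 1.96 × √(0.49/108) = 13.2 points.
- Rates 0.7 and 0.6: 1.96 × √(0.45/108) = 12.7 points.

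This is a Wald approximation used for scale only; the planned interval is Miettinen-Nurminen.

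**The case against.** The strongest reply is that this is a drafting slip with one sensible reading. Above and below were evidently meant to split all subjects in two, and nothing shows that anyone intended or programmed a third group of automatic non-responders. The protocol and SAP 11.3 already define MN correctly, and SAP section 16 declares no change to MN seroconversion, so 8.7 was probably not meant to depart from them. No passage ranks 8.7 above 11.3. The route from MN to a primary endpoint needs a strain to fail agglutination and the 8.7 wording to be the one applied. The size rests wholly on assumed inputs. The study has no hypothesis test and no success criterion. Editing the protocol also carries approval overheads.

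Most of this is fair and limits the weight of the point. The likely intent is clear, the size is unknown, the MN route is only a possibility, and no decision rule is at risk. It does not remove the defect. SAP 8.7 is where the derived variable is specified, and it has an explicit default of 0. Code that follows it exactly returns a wrong value for a primary endpoint without any error message. For HI, no other passage gives the correct boundary.

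**Conclusion.** The concern holds. The HI rule gives the wrong code to any subject with a baseline of exactly 1:10 who reaches 1:40 or more, in all three places where it is stated. The MN rule in SAP 8.7 has the same gap and contradicts SAP 11.3 and Protocol 8.1.2.2.

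The harm, if the text is programmed literally, is a downward bias in reported seroconversion rates. It could be negligible or reach several points per arm, depending on a baseline distribution that the documents do not give. The shift in between-arm differences is likely to be small against a half-width of about 13 points, provided the arms have similar shares at 1:10. GMT, GMFI and the percentage at or above 1:40 do not use this variable and are unaffected. This should be fixed, but it does not threaten the study's main conclusions.

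**What to change.** - **HI:** in SAP 8.7, SAP 11.2 and Protocol 8.1.1.1, change the upper branch to baseline at or above the LLOQ (≥ 1:10).
- **MN:** in SAP 8.7, change the upper branch to baseline ≥ LLOQ, so that it matches SAP 11.3 and Protocol 8.1.2.2.
- **Code:** check the one derivation line for each assay. Add test records with baseline 10 and post titre 40 for HI, and baseline LLOQ and post titre 4 × LLOQ for MN. Both must return 1.
- **Record:** list the clarification in SAP section 16.

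The cost is one phrase per rule and a short code check, with no new data. The SAP edits alone settle the derivation. The protocol edit appears to fit the minor clarification route in Protocol 13.4, which is for the sponsor to confirm.
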